## 6.3 Randomization

Only subjects who have completed screening assessments and are eligible for participation in the study (and completed the Run-in Period and qualify to enter the Treatment Period [Part 2]) will be randomized to receive active study drug or placebo or active control during the Treatment Period.

Randomization will be stratified by ppFEV1 determined during screening (Day -28 to Day -1 assessment; <70 versus ≥70) in Parts 1 [REDACTED] and the TEZ/IVA Run-in Period (Day -14 assessment; <70 versus ≥70) in Part 2. If the Day -14 ppFEV1 value is not valid or not available, the most recent available ppFEV1 value before the date of randomization will be used for stratification.

An interactive web response system (IWRS) will be used to assign subjects to treatment.

## 6.4 Blinding and Unblinding

Please refer to Section 10.7 of the CSP for details.

## 7 ANALYSIS SETS

The following analysis sets are defined: All Subjects Set, Full Analysis Set and Safety Set.

### 7.1 All Subjects Set

The **All Subjects Set** is defined as all subjects who were randomized or received at least 1 dose of study drug. The All Subjects Set will be used for individual subject data listings and disposition summary tables, unless otherwise specified.

## 7.2 Full Analysis Set

The **Full Analysis Set** (FAS) will include all randomized subjects who carry the intended *CFTR* genotype and have received at least 1 dose of study drug in the Treatment Period. The FAS will be used for all PD and efficacy analyses in which subjects will be analyzed according to their randomized treatment group, unless otherwise specified.

## 7.3 Safety Set

### 7.3.1 Parts 1 [REDACTED]

The **Safety Set** will include all subjects who received at least 1 dose of study drug. The Safety Set will be used for all safety analyses, unless otherwise specified. Subjects will be analyzed according to the treatment they received.

For subjects receiving study drug from more than one treatment group, the treatment group allocation will be the higher treatment group (in the increasing priority order: Triple placebo, TC-5 mg, TC-10mg, TC-20 mg).

### 7.3.2 Part 2

The **Safety Set for the Run-in Period** will include all subjects who received at least 1 dose of study drug TEZ/IVA in the Run-in Period. This Safety Set will be used for individual subject data listings for the Run-in Period, unless specified otherwise.

The **Safety Set for Treatment Period** will include all subjects who received at least 1 dose of study drug in the Treatment Period. This Safety Set will be used for all safety analyses for the Treatment Period, unless specified otherwise.

For subjects receiving study drug from more than one treatment group, the treatment group allocation will be the higher treatment group (VX-121/TEZ/VX-561 > TEZ/IVA).

## 8 STATISTICAL ANALYSIS

### 8.1 General Considerations

The Schedule of Assessments is provided in Section 3 of the CSP. The precision standards for reporting safety, efficacy and PD variables are provided in an internal Biometrics document that specifies the programming rules including the precision for variables.

The analysis will be performed for each part, and presented separately for each part by treatment group, for the Treatment Period, unless specified otherwise. The treatment groups are defined as follows:

- Part 1:
  - Placebo
  - TC-5 mg (presented as “VX-121 5 mg qd/TEZ 100 mg qd/VX-561 150 mg qd” in tables, figures, listings (TFLs))
  - TC-10 mg (presented as “VX-121 10 mg qd/TEZ 100 mg qd/VX-561 150 mg qd” in TFLs)
  - TC-20 mg (presented as “VX-121 20 mg qd/TEZ 100 mg qd/VX-561 150 mg qd” in TFLs).

- Part 2:
  - Placebo + TEZ/IVA (presented as “Placebo/TEZ 100 mg qd/IVA 150 mg q12h” in TFLs)
  - TC-20 mg (presented as “VX-121 20 mg qd/TEZ 100 mg qd/VX-561 150 mg qd” in TFLs).

All individual subject data for those randomized or dosed with study drug will be presented in data listings.

**Continuous variables** will be summarized using the following descriptive summary statistics: the number of subjects (n), mean, SD, median, minimum value (min), and maximum value (max).

**Categorical variables** will be summarized using counts and percentages. Percentages will be presented to 1 decimal place.

**Treatment-emergent (TE) period** for Parts 1 [REDACTED] will include the time from the first dose of study drug in the Treatment Period until 28 days after the last dose date of study drug (from treatment period or washout period) or the completion date of study participation (obtained from the end of follow-up page of the CRF), whichever occurs first.

For Part 2, the TE period will be defined separately for the Run-In Period, and the Treatment Period:

- The TE period for the Run-in Period will include the time from the first dose of study drug in the Run-in Period to: (1) the first dose of study drug in the Treatment Period for subjects who complete the Run-in Period and continue to the Treatment Period, or (2) 28 days after the last dose of study drug in the Run-in Period or the completion date of study participation (obtained from the end of follow-up page of the CRF), whichever occurs first, for subjects who do not continue to the Treatment Period.
- The TE period for the Treatment Period will include the time from the first dose of study drug in the Treatment Period to 28 days after the last dose of study drug (from treatment period or washout period) or the completion date of study participation (obtained from the end of follow-up page of the CRF), whichever occurs first.

**Baseline value**, unless otherwise specified, will be defined as the most recent non-missing measurement (scheduled or unscheduled) collected before the first dose of study drug in the Treatment Period. For ECG, baseline will be defined as the most recent non-missing measurement (or the average of triplicate measurements, if the most recent non-missing measurement is obtained in triplicate), before the first dose of study drug in the Treatment Period.

**Absolute change** from baseline will be calculated as postbaseline value – baseline value.

**Relative change** from baseline will be calculated as (postbaseline value – baseline value)/baseline value.

**Unscheduled visits:** Unscheduled visit measurements will be included in analysis as follows:

- In scheduled visit windows per specified visit windowing rules
- In the derivation of baseline
- In the derivation of maximum and minimum values during TE period, and maximum and minimum change from baseline values for safety analyses
- In individual subject data listings as appropriate

**Visit windowing rules:** The analysis visit windows for protocol-defined visits are provided in [Appendix A](#).

Spirometry (ppFEV1) will be used for both efficacy and safety purposes. For efficacy analysis, the assessments will follow the visit windowing rules for efficacy. For safety analysis, the nominal visits will be used for ppFEV1 collected at both pre-dose on Day 1 and pre-dose on Day 2 (for Part 1 only).

**Incomplete/missing data** will not be imputed, unless specified otherwise.

**Outliers:** No formal statistical analyses will be performed to detect or remedy the presence of statistical outliers.

**Multiplicity:** There will be no multiplicity adjustment for performing multiple hypothesis tests.

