## 8.2 Background Characteristics

### 8.2.1 Subject Disposition

The number of subjects in the following categories will be presented by treatment group and overall for Parts 1 ██████:

- All Subjects Set;
- Randomized;
- Safety Set;
- Full Analysis Set;
- Randomized but not dosed.

The number of subjects for the Treatment Period in the following categories will be presented by treatment group and overall for Part 2:

- Randomized or dosed in the Treatment Period;
- Randomized;
- Safety Set for the Treatment Period;
- Full Analysis Set;
- Randomized but not dosed in the Treatment Period.

The number and percentage (based on FAS) of subjects in each of the following disposition categories will be presented by treatment group and overall:

- Completed study drug treatment (Separated by Treatment Period and Washout Period for all parts);
- Prematurely discontinued treatment and the reason for discontinuation (i.e., discontinued all study drugs) (Separated by Treatment Period and Washout Period for all parts);
- Completed study (i.e., completed Safety Follow-up Visit);
- Prematurely discontinued the study and the reason for discontinuation.

A separate disposition table will be provided for the Run-in Period in Part 2 with the following categories:

- All Subjects Set
- Safety Set for the Run-in Period

The number and percentage (based on Safety Set for the Run-in Period) of subjects in each of the following disposition categories will be presented:

- Completed treatment in the Run-in Period;
- Prematurely discontinued treatment during run-in and the reason for treatment discontinuation;
- Prematurely discontinued study during run-in and the reason for study discontinuation.

A listing will be provided by part, for subjects who discontinued treatment (including the Run-in Period in Part 2) or who discontinued study with reasons for discontinuation.

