### 8.4.1 Adverse Events

For Parts 1 [REDACTED]

For analysis purposes, AEs will be classified as pretreatment AEs, TEAEs, or post-treatment AEs, defined as follows:

**Pretreatment AE:** any AE that started before the first dose date of study drug

**TEAE:** any AE that worsened (either in severity or seriousness) or that was newly developed at or after the first dose date of study drug through the end of the TE period.

**Post-treatment AE:** any AE that worsened (either in severity or seriousness) or that was newly developed after the TE period

For Part 2:

For analysis purposes, AEs will be classified as pretreatment AEs, TEAEs during the Run-in Period, TEAEs during the Treatment Period, and post-treatment AEs, defined as follows:

**Pretreatment AE:** any AE that started before the first dose date of study drug (TEZ/IVA) in the Run-in Period.

**TEAE during the Run-in Period:** any AE that worsened (either in severity or seriousness) or that was newly developed at or after the first dose date of study drug (TEZ/IVA) through the end of the TE period for the Run-in Period.

**TEAE during the Treatment Period:** any AE that worsened (either in severity or seriousness) or that was newly developed at or after the first dose date of study drug (TC or placebo+TEZ/IVA) through the end of the TE period for the Treatment Period.

**Post-treatment AE:** any AE that worsened (either in severity or seriousness) or that was newly developed after:

- the TE period for Run-in Period if the subject did not receive treatment in the Treatment Period, or
- the TE period for the Treatment Period if the subject received treatment in the Treatment Period.

For AEs with completely missing or partially missing start dates, if there is no clear evidence that the AEs started before or after study treatment for Parts 1 [REDACTED] or if there is no clear evidence that the AEs are pre-treatment or TEAE during the Run-in Period or post-treatment for Part 2, the AEs will be classified as TEAEs during the Treatment Period. Unless otherwise specified, TEAE refers to TEAE during the Treatment Period.

Details for imputing missing or partial start dates of adverse events are described in [Appendix D](#).

AE summary tables will be presented for TEAEs only, for the TE period for Parts 1 [REDACTED] and the TE period for Treatment Period in Part 2.

An overview of all TEAEs by treatment group and overall will be summarized in the following categories:

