- Number of TEAEs (total number of TEAEs only);
- Subjects with any TEAEs;
- Subjects with TEAEs by strongest relationship;
- Subjects with TEAEs by maximum severity;
- Subjects with TEAEs leading to study drug discontinuation (discontinuation of any study drug);
- Subjects with TEAEs leading to study drug interruption (interruption of any study drug);
- Subjects with Grade 3/4 TEAEs;
- Subjects with related TEAEs;
- Subjects with serious TEAEs;
- Subjects with related serious TEAEs;
- Subjects with TEAE leading to death.

The following summary tables of TEAEs will be presented by treatment group:

- All TEAEs
- Grade 3/4 TEAEs
- TEAEs by strongest relationship
- TEAEs by maximum severity
- TEAEs leading to treatment discontinuation
- TEAEs leading to treatment interruption
- Related TEAEs
- Serious TEAEs
- Related serious TEAEs
- TEAEs leading to death

Summaries will be presented by MedDRA System Organ Class (SOC) and Preferred Term (PT) using frequency counts and percentages (i.e., number and percentage of subjects with an event). When summarizing the number and percentages of subjects, subjects with multiple occurrences of the same adverse event or a continuing adverse event will be counted once, and only the maximum severity level will be presented in the severity summaries, and the strongest relationship level in the relationship summaries.

Additional summary tables will be presented by treatment group and by PT for TEAEs showing number and percentage of subjects.

All AEs, including pre-treatment AEs, TEAEs for all applicable periods, and post-treatment AEs, will be presented in an individual subject data listing based on the All Subjects Set. In addition, separate listings containing individual subject adverse event data for TEAEs leading to treatment discontinuation, TEAEs leading to treatment interruption, Grade 3/4 TEAEs, SAEs and all deaths will be provided separately, with a flag indicating the TEAE status for SAEs and deaths.

In addition, the following tables for the Run-in period will be presented by overall based on the Safety Set for the Run-in period.

- An overview of TEAEs during the Run-in Period
- All TEAEs during the Run-in Period by SOC and PT

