#### **8.4.2 Clinical Laboratory**

For the treatment-emergent laboratory assessments, the observed values and changes from baseline values of the continuous hematology, chemistry, and coagulation results will be summarized in SI units at each scheduled visit, by treatment group for each part.

The number and percentage of subjects meeting at least 1 threshold analysis criterion event, during the TE period for Parts 1 [REDACTED] or the TE period for Treatment Period for Part 2, will be summarized by treatment group for each part. The threshold analysis criterion shift from baseline will also be summarized for selected laboratory parameters. The threshold analysis criteria are provided in [Appendix E](#).

For selected LFT laboratory test (alanine aminotransferase [ALT], aspartate aminotransferase [AST], alkaline phosphatase [ALP], and total bilirubin), a scatter plot of the maximum treatment-emergent value versus the baseline value corresponding to  $\times$ ULN will be presented. Further, a scatter plot of the maximum treatment-emergent value of ALT and AST, separately, versus the maximum treatment-emergent value of total bilirubin corresponding to  $\times$ ULN will also be presented by treatment group, for each part.

Results of abnormal urinalysis and positive urine/serum pregnancy test will be listed in individual subject data listings only.

In addition, a listing containing individual subject hematology, chemistry, and coagulation values will be provided. This listing will include data from both scheduled and unscheduled visits.

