#### **8.4.5 Pulse Oximetry**

For the treatment-emergent pulse oximetry measurements, a summary of observed values and changes from baseline values will be provided at each scheduled visit, for the percent of oxygen saturation, by treatment group, for each part.

The number and percentage of subjects with shift changes from baseline (normal/missing and low according to the reference range) to the lowest percent of oxygen saturation during the TE

Period for Parts 1 [REDACTED] or the TE period for the Treatment Period for Part 2 will be summarized by treatment group, for each part.

[figure not shown]
In addition, a listing containing individual subject pulse oximetry values will be provided for each part. This listing will include data from both scheduled and unscheduled visits.

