			drug administration date from EX SDTM domain, as appropriate, The imputation algorithm will ensure the imputed last dose date does not exceed Day 29 visit date.
			4. Sweat Chloride:  Non-missing sweat chloride concentrations from the left arm and right arm with the assessment end date/time for a given arm up to 30 minutes after first dose time in treatment period will be considered for baseline.
			5. Electrocardiogram:  Baseline is defined as the most recent pretreatment measurement before the first dose of study drug in the Treatment Period (or the average of triplicate measurements, if the most recent non-missing measurement is obtained in triplicate). If multiple ECG measurements are obtained on the same calendar day during the TE period, 
 
○ For summary purpose, the calculated average ECG will be used as the ECG value on that day;
 
○ For threshold analysis purpose, all reported ECG values will be used.
 

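### TEAE tables pool events on VX-121 with events in Washout and follow-up under the VX-121 dose label; a supplementary table by onset period would separate them

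*SAP*

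**What the plan says.** In both parts the last VX-121 dose is the morning dose at Day 29 (Protocol Tables 3-1 and 3-2, dosing footnotes). In Part 1 the TC arms then stay on TEZ/VX-561, and the placebo arm on dual placebo, to the Washout Visit at Day 47. In Part 2 both arms take TEZ/IVA to Day 57, and Protocol 10.7 makes that period open-label.

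SAP 8.1 carries the TE period across this change. In Part 1 it lasts "until 28 days after the last dose date of study drug (from treatment period or washout period"). In Part 2 it runs from the first Treatment Period dose "to 28 days after the last dose of study drug (from treatment period or washout period"). In both parts study completion ends it if that comes first. This agrees with Protocol 12.3.1.

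SAP 8.1 has a general default to the Treatment Period, but SAP 8.4 replaces it with the TE period for all safety analyses. The TEAE tables in SAP 8.4.1 report the "number and percentage of subjects with an event" by treatment group. The only TEAE tables for a separate period are two for the Part 2 Run-in, before any VX-121. For Part 2 the SAP adds: "Unless otherwise specified, TEAE refers to TEAE during the Treatment Period". The group labels in SAP 8.1 carry the VX-121 dose. Disposition, by contrast, is reported "Separated by Treatment Period and Washout Period for all parts" (SAP 8.2.1).

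**The concern.** Safety and tolerability of VX-121 in TC is the first primary objective, and SAP 8.4 makes safety purely descriptive. The TEAE tables are therefore the main safety result, not a supplement to a test.

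Only the TC arms lose VX-121 at Day 29. An event while VX-121 is taken and an event after step-down mean different things for the drug, yet both enter the same cell. In Part 2 an AE starting on, say, Day 50 on open-label TEZ/IVA is counted as a Treatment Period TEAE under the VX-121 20 mg label. Exposure is summarized for the Treatment Period only (SAP 8.2.5), so an event count over 75 or 85 days sits beside an exposure summary of about 29 days. If a TC arm shows an excess, the planned tables cannot say when it arose.

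**Working it through.** **Inputs.** Last VX-121 dose: Day 29 (± 2). Last Washout dose: Day 47 (± 3) in Part 1 and Day 57 (± 3) in Part 2. Tail: 28 days (SAP 8.1). Arms: 18, 18 and 9 on TC in Part 1 and 18 in Part 2. These sum to 18 + 18 + 9 + 18 = 63, the number in SAP 6.2. The plan gives no figure for the length of the TE period, so there is none to reproduce.

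**Nominal composition.** TE end = last Washout dose day + 28.

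| | TE days | On VX-121 | Washout | Follow-up |
|---|---|---|---|---|
| Part 1 | 47 + 28 = 75 | 29 (39%) | 47 − 29 = 18 (24%) | 28 (37%) |
| Part 2 | 57 + 28 = 85 | 29 (34%) | 57 − 29 = 28 (33%) | 28 (33%) |

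Days after the last VX-121 dose are thus 46/75 = 61% in Part 1 and 56/85 = 66% in Part 2.

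**What the Washout doses add.** A 28-day tail from the last VX-121 dose alone would end at Day 29 + 28 = 57. Counting Washout doses lengthens the period by 75 − 57 = 18 days in Part 1 and 85 − 57 = 28 days in Part 2. The other 28 days after VX-121 equal an ordinary post-dose tail.

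**Visit windows, full 28-day tail.** The on-VX-121 share is 27/78 = 35% to 31/72 = 43% in Part 1, and 27/88 = 31% to 31/82 = 38% in Part 2.

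**Part 2 without a Safety Follow-up.** Protocol 9.1.5 waives that visit for subjects who move to a commercial CFTR modulator within 28 days of Day 57. If completion is then recorded at Day 57 (an assumption; Protocol 13.1.1.3 allows AE collection for up to 35 days after the last dose), the share after VX-121 is 28/57 = 49%, not 66%.

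**Illustration of size.** These rates are assumed, not taken from the documents: 10% background risk over 29 days, constant hazard, arm of 18.

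- Risk doubled on VX-121 only, counted over the on-drug window: (0.20 − 0.10) × 18 = 1.8 extra subjects.
- The same effect in the pooled table, Part 1: control 1 − 0.9^(75/29) = 0.2385; TC 1 − 0.8 × 0.9^(46/29) = 0.3231; difference 0.0846 × 18 = 1.5.
- The same, Part 2: 0.3473 − 0.2657 = 0.0816; × 18 = 1.5.
- Hazard doubled in the Washout only, pooled table, Part 1: 1 − 0.9^(93/29) = 0.2867; 0.2867 − 0.2385 = 0.0482; × 18 = 0.9.
- The same, Part 2: 1 − 0.9^(113/29) = 0.3367; 0.3367 − 0.2657 = 0.0710; × 18 = 1.3.

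Halve these for an arm of 9. Pooling costs 1.8 − 1.5 = 0.3 subjects of signal. But an on-drug excess of 1.5 and a step-down excess of 0.9 to 1.3 look alike in a pooled cell.

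**The case against.** A TE period with a post-dose tail is standard, it is the protocol's own definition, and every arm has the same window, so the arms remain comparable. This stands, and the whole-TE tables should stay. A reader might infer that the SAP departs from the protocol or that the period is wrong; the two documents agree.

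Day 29 is not an on/off boundary. Protocol 9.3.1 uses the Part 1 Washout to study VX-121 as it washes out, and no half-life is given. This also stands. A reader might take the 61% and 66% as drug-free time; those shares include the ordinary 28-day tail and days with residual VX-121.

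Other outputs help. Disposition is split by period. By-visit rows at Day 47 (Part 1) and Days 43 and 57 (Part 2) cover several assessments, including spirometry. Relatedness tables bear on causality, and the listings allow AEs to be read by subject in arms of 9 to 18. All true, but none gives TEAE counts by period. A split made from the listings afterwards would have no pre-specified boundaries, denominators or rule for partial dates.

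Two stronger readings go too far. The threshold tables ("The number and percentage of subjects meeting at least 1 threshold analysis criterion event") and the oximetry shift table ("The number and percentage of subjects with shift changes from baseline") also span the whole TE period, so a reader might want them split too. The day shares do not carry over to scheduled measurements: for Part 1 laboratory tests, ECG and weight only 1 of 4 scheduled post-baseline visits, the follow-up, comes after VX-121. Splitting these tables would add complexity for little gain. A reader might also infer that the partial-date imputation in SAP Appendix D distorts the planned TEAE counts. Moving a start date from after Day 29 to an earlier day on treatment leaves the event inside the TE period; it matters only once a split is made.

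**Conclusion.** The point holds for the TEAE tables: they pool time on VX-121, Washout and follow-up under the VX-121 dose label, and nothing else planned counts TEAEs by period. Nominally 39% of TE days in Part 1 and 34% in Part 2 are on VX-121, assuming visits on target days and the full tail. No hypothesis test is affected. The expected effect is about one subject or so per arm under the assumed rates above, so what a split adds is attribution, not precision. It is a worthwhile, inexpensive improvement to the reporting of a primary objective, not a flaw that invalidates the safety analysis.

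**What to change.** Keep the whole-TE tables as the main tables. Add to SAP 8.4.1 a supplementary TEAE overview and SOC/PT table by onset period:

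- (a) first through last Treatment Period dose;
- (b) the day after, through the last Washout dose;
- (c) the rest of the TE period.

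Use as denominators the subjects who entered each period. Place an AE that is treatment-emergent through worsening by the date it worsened; the TEAE definition already requires that date. Put AEs whose partial start date fits more than one period in an undetermined row, not in a period chosen by Appendix D imputation. The end of (a) is already derived in SAP Appendix A, where a missing date is handled so that "The imputation algorithm will ensure the imputed last dose date does not exceed Day 29 visit date". Leave the threshold and shift tables as planned.

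The cost is a few more descriptive tables with small counts. No visit, data item or protocol definition changes. Periods (b) and (c) may contain residual VX-121, and (b) also contains the background drugs, so the split must be read together with the whole-TE table.
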